7.5.4. Medically Attended Adverse Events

A MAAE is an AE that leads to an unscheduled visit to an HCP. This would include visits to a study site for unscheduled assessments (eg, abnormal laboratory test results follow-up, COVID-19 [Section 7.4.1]) and visits to HCPs external to the study site (eg, urgent care, primary care physician). Investigators will review unsolicited AEs for the occurrence of any MAAE. Unsolicited AEs will be captured on the AE page of the eCRF.

All confirmed symptomatic COVID-19 cases (Section 7.4.1) will be recorded as MAAEs and reported to the Sponsor or designee immediately and in all circumstances within 24 hours, using the SAE Mailbox, the SAE Hotline, or the SAE Fax line (Section 7.5.11). The investigator will submit any updated COVID-19 case data to the Sponsor within 24 hours of it being available.

7.5.4.1. Anaphylaxis

All suspected cases of anaphylaxis should be recorded as MAAEs and reported as SAEs (Section 7.5.2) based on criteria for a medically important event unless the event meets other serious criteria. As an SAE, the event should be reported to the Sponsor or designee immediately and in all circumstances within 24 hours as per Section 7.5.10 (Reporting SAEs). The investigator will submit any updated anaphylaxis case data to the Sponsor within 24 hours of it being available. For reporting purposes, a participant who displays signs/symptoms consistent with anaphylaxis as shown below should be reported as a potential case of anaphylaxis. This is

provided as general guidance for investigators and is based on the Brighton Collaboration case definition ([Rüggeberg et al 2007](#)).

Anaphylaxis is an acute hypersensitivity reaction with multi-organ-system involvement that can present as or rapidly progress to a severe life-threatening reaction. It may occur following exposure to allergens from a variety of sources. Anaphylaxis is a clinical syndrome characterized by:

- Sudden onset AND
- Rapid progression of signs and symptoms AND
- Involving 2 or more organ systems, as follows:
 - **Skin/mucosal:** urticaria (hives), generalized erythema, angioedema, generalized pruritus with skin rash, generalized prickle sensation, red and itchy eyes
 - **Cardiovascular:** measured hypotension, clinical diagnosis of uncompensated shock, loss of consciousness or decreased level of consciousness, evidence of reduced peripheral circulation
 - **Respiratory:** bilateral wheeze (bronchospasm), difficulty breathing, stridor, upper airway swelling (lip, tongue, throat, uvula, or larynx), respiratory distress, persistent dry cough, hoarse voice, sensation of throat closure, sneezing, rhinorrhea
 - **Gastrointestinal:** diarrhea, abdominal pain, nausea, vomiting

7.5.5. Adverse Events of Special Interest

An AESI is an AE (serious or nonserious) of scientific and medical concern specific to the Sponsor's product or program, for which ongoing monitoring and immediate notification by the investigator to the Sponsor is required and documentation is in the form of a case narrative. Such events may require further investigation to characterize and understand them. Refer to [Section 10.4](#), Appendix 4 for a list of AESIs pertinent to this study. All AESIs will be collected throughout the entire study period and must be reported to the Sponsor or designee immediately and in all circumstances within 24 hours of becoming aware of the event via the EDC system. If a site receives a report of a new AESI from a study participant or receives updated data on a previously reported AESI and the eCRF has been taken offline, then the site can report this information on a paper AESI form using the SAE Mailbox, the SAE Hotline, or the SAE Fax line ([Section 7.5.11](#)).

7.5.5.1. Acute Myocarditis and/or Pericarditis

These definitions are intended to serve as a guide to help in the reporting of suspected cases of myocarditis and/or pericarditis; however, the diagnosis of suspected cases is left to the investigator's clinical judgment.

The investigator's medical judgment must be applied when parent(s)/LAR(s) report that a participant has symptoms concerning for myocarditis and/or pericarditis per the CDC case definition. Diagnostic evaluation (eg, EKG, echocardiogram) and laboratory testing (eg, troponin) per the CDC definition of myocarditis and/or pericarditis must be promptly obtained

for any participant with concerning signs/symptoms. Referral to a pediatric cardiologist should be obtained in those with positive test results or clinically significant symptoms without other identifiable causes. Additional testing and evaluation may be indicated. Once available, updated myocarditis, pericarditis, or myopericarditis case data will be submitted by the investigator to the Sponsor within 24 hours.

All suspected cases of probable and confirmed myocarditis, pericarditis, or myopericarditis should be recorded as an AESI, and reported as an SAE, if the event meets seriousness criteria. As an SAE, the event should be reported to the Sponsor or designee immediately and in all circumstances within 24 hours as per [Section 7.5.12](#). The investigator will submit any updated myocarditis, pericarditis, or myopericarditis case data to the Sponsor within 24 hours of it being available. For reporting purposes, a participant who displays signs/symptoms consistent with the CDC case definitions as described below ([Gargano et al 2021](#)), should be reported as a potential case of confirmed or probable myocarditis, pericarditis, or myopericarditis.

7.5.5.2. Acute Myocarditis Case Definition

Presence of ≥ 1 new or worsening of the following clinical symptoms (persons who lack the listed symptoms but who meet other criteria may be classified as subclinical myocarditis [probable or confirmed]):

- Chest pain/pressure/discomfort
- Dyspnea/shortness of breath/pain with breathing
- Palpitations
- Syncope

OR

Infants and children aged <12 years might instead have ≥ 2 of the following symptoms:

- Irritability
- Vomiting
- Poor feeding
- Tachypnea
- Lethargy

AND

For PROBABLE CASE:

Presence of ≥ 1 new finding of the following:

- Troponin level above upper limit of normal (any type of troponin)
- Abnormal ECG or EKG or rhythm monitoring findings consistent with myocarditis
 - To meet the ECG or rhythm monitoring criterion, a probable case must include at least one of the following:
 - ST segment or T-wave abnormalities

- Paroxysmal or sustained atrial, supraventricular, or ventricular arrhythmias
- AV nodal conduction delays or intraventricular conduction defects
- Abnormal cardiac function or wall motion abnormalities on echocardiogram
- Cardiac MRI finding consistent with myocarditis ([Ferreira et al 2018](#))

AND

- No other identifiable cause of the symptoms and findings

For CONFIRMED CASE:

- Histopathologic confirmation of myocarditis (using Dallas criteria [[Aretz et al 1987](#)])

OR

- Cardiac magnetic resonance imaging findings consistent with myocarditis in the presence of troponin level above upper limit of normal (any type of troponin)

AND

- No other identifiable cause of the symptoms and findings

7.5.5.3. Acute Pericarditis Case Definition

Presence of ≥ 2 new or worsening of the following clinical features ([Adler et al 2015](#)):

- Acute chest pain (Typically described as pain made worse by lying down, deep inspiration, or cough; and relieved by sitting up or leaning forward, although other types of chest pain may occur)
- Pericardial rub on examination
- New ST-elevation or PR-depression on EKG
- New or worsening pericardial effusion on echocardiogram or magnetic resonance imaging

7.5.5.4. Myopericarditis Case Definition

Participants who meet criteria for both myocarditis and pericarditis may be described under myopericarditis.

7.5.5.5. Multisystem Inflammatory Syndrome in Children Case Definition

Investigators will also be asked to report, as AESI, clinical signs/symptoms consistent with the CDC case definition of MIS-C (<https://emergency.cdc.gov/2020/han00432.asp>):

- An individual aged < 21 years presenting with fever, laboratory evidence of inflammation, and evidence of clinically severe illness requiring hospitalization, with multisystem (> 2) organ involvement (cardiac, renal, respiratory, hematologic, gastrointestinal, dermatologic or neurological);

AND

- No alternative plausible diagnoses;

AND

- Positive for current or recent SARS-CoV-2 infection by RT-PCR, serology, or antigen test; or COVID-19 exposure within the 4 weeks prior to the onset of symptoms:
 - Fever $\geq 38.0^{\circ}\text{C}/\geq 100.4^{\circ}\text{F}$ for ≥ 24 hours, or report of subjective fever lasting ≥ 24 hours
 - Including, but not limited to, one or more of the following: an elevated CRP, ESR, fibrinogen, procalcitonin, d-dimer, ferritin, LDH, or IL-6, elevated neutrophils, reduced lymphocytes, and low albumin

Some individuals may fulfill full or partial criteria for Kawasaki disease but should be reported if they meet the case definition for MIS-C. Consider MIS-C in any pediatric death with evidence of SARS-CoV-2 infection.

All cases of MIS-C will be reported to the Sponsor or designee immediately and in all circumstances within 24 hours, using the SAE Mailbox, the SAE Hotline, or the SAE Fax line ([Section 7.5.11](#)).

7.5.6. Recording and Follow-up of Pregnancy

Female individuals who have a positive pregnancy test at Screening should not be enrolled; participants who have a positive pregnancy test any time during the study should receive no further dosing with IP but should be asked to remain in the study and be monitored for safety.

Details of all pregnancies in female participants will be collected after the start of study treatment and until the end of their participation in the study.

- If a pregnancy is reported, the investigator should inform the Sponsor within 24 hours of learning of the pregnancy and should follow the procedures outlined in this section.
- Abnormal pregnancy outcomes (eg, spontaneous abortion, fetal death, stillbirth, congenital anomalies, ectopic pregnancy) are considered SAEs.

Pregnancies occurring in participants after enrollment must be reported to Sponsor or designee within 24 hours of the study site learning of its occurrence, using the SAE Mailbox, the SAE Hotline, or the SAE Fax line ([Section 7.5.11](#)). If the participant agrees to submit this information, the pregnancy must be followed to determine the outcome, including spontaneous or voluntary termination, details of the birth, and the presence or absence of any birth defects, congenital abnormalities, or maternal and/or newborn complications. This follow-up should occur even if intended duration of the safety follow-up for the study has ended. Pregnancy report forms will be distributed to the study site to be used for this purpose. The investigator must immediately (within 24 hours of awareness) report to the Sponsor any pregnancy resulting in an abnormal outcome according to the procedures described for SAEs.

7.5.7. Eliciting and Documenting Adverse Events

The investigator is responsible for ensuring that all AEs and SAEs are recorded in the eCRF and reported to the Sponsor.

Solicited ARs will be collected from Day 1 through 7 days after each dose in Part 1A, Part 1C, Part 2, and Part 3. Other (unsolicited) AEs will be collected from Day 1 through 28 days after each dose in Part 1A, Part 1C, Part 2, and Part 3.

Both MAAEs and SAEs will be collected from participants as specified in the SoA until the end of their participation in Part 1A, Part 1B, Part C, Part 2, and Part 3. Any AEs that occur before administration of IP will be analyzed separately from AEs.

At every study site visit or telephone contact, participants will be asked a standard question to elicit any medically related changes in their well-being (including COVID-19 symptoms) according to the scripts provided. Participants will also be asked if they have been hospitalized, had any accidents, used any new medications, changed concomitant medication regimens (both prescription and over-the-counter medications), or had any nonstudy vaccinations.

In addition to participant observations, physical examination findings, or data relevant to participant safety classified as an AE will be documented on the AE page of the eCRF.

After the initial AE/SAE report, the investigator is required to proactively follow each participant at subsequent visits/contacts. All AEs and SAEs will be treated as medically appropriate and followed until resolution, stabilization, the event is otherwise explained, or the participant is LTFU (as defined in [Section 6.4](#)).

7.5.8. Assessment of Intensity

An event is defined as “serious” when it meets at least one of the predefined outcomes as described in the definition of an SAE ([Section 7.5.2](#)), NOT when it is rated as severe.

The severity (or intensity) of an AR or AE refers to the extent to which it affects the participant’s daily activities. The Toxicity Grading Scale for Healthy Adult and Adolescent Volunteers Enrolled in Preventative Vaccine Clinical Trials ([DHHS 2007](#)) will be used to categorize local and systemic reactogenicity events (solicited ARs), and vital sign measurements observed during this study. Specific criteria for local and systemic reactogenicity events are presented in [Section 7.5.3](#).

The determination of severity for all unsolicited AEs should be made by the investigator based upon medical judgment and the definition of severity as follows:

- Mild: These events do not interfere with the participant’s daily activities.
- Moderate: These events cause some interference with the participant’s daily activities and require limited or no medical intervention.
- Severe: These events prevent the participant’s daily activity and require intensive therapeutic intervention.

Study staff should elicit from the participant the impact of AEs on the participant’s activities of daily living to assess severity and document appropriately in the participant’s source documentation. Changes in the severity of an AE should be documented in the participant’s source documentation to allow an assessment of the duration of the event at each level of intensity to be performed. An AE characterized as intermittent requires documentation of onset and duration of each episode. An AE that fluctuates in severity during the course of the event is reported once in the eCRF at the highest severity observed.

7.5.9. Assessment of Causality

The investigator's assessment of an AE's relationship to IP is part of the documentation process but is not a factor in determining what is or is not reported in the study.

The investigator will assess causality (ie, whether there is a reasonable possibility that the IP caused the event) for all AEs and SAEs. The relationship will be characterized using the following classification:

Not related: There is not a reasonable possibility of a relationship to the IP. Participant did not receive the IP OR temporal sequence of the AE onset relative to administration of the IP is not reasonable OR the AE is more likely explained by another cause than the IP.

Related: There is a reasonable possibility of a relationship to the IP. There is evidence of exposure to the IP. The temporal sequence of the AE onset relative to the administration of the IP is reasonable. The AE is more likely explained by the IP than by another cause.

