In addition to the increased incidence and hospitalizations observed, COVID-19 disease in children and adolescents can include MIS-C, a unique complication in conjunction with severe disease ([Vogel et al 2021](#)). MIS-C shares some common features with Kawasaki disease, and is defined as fever, laboratory evidence of inflammation, and involvement of ≥ 2 organ systems in an individual <21 years of age with no plausible alternative diagnosis and evidence of current or recent SARS-CoV-2 infection. MIS-C is also associated with cardiac complications. Through 01 Aug 2022, 8798 cases of MIS-C have been reported in the USA, with 71 MIS-C related deaths reported. The median age of patients with MIS-C was 9 years (range 5 to 13 years) ([CDC 2022d](#)).

Myocarditis has been well described as a complication of pediatric COVID-19. Children under 16 years of age with COVID-19 are at an almost 37-fold higher risk of myocarditis than the uninfected age- and gender-matched control population ([Boehmer et al 2020](#)). Of note, the frequency of myocarditis due to COVID-19 is higher than that of vaccine-associated myocarditis. Additionally, the clinical syndrome of COVID-19 related myocarditis is more severe and clinically meaningful than vaccine-associated myocarditis. Patients with vaccine-associated myocarditis generally have a milder clinical course than patients with classic

myocarditis or MIS-C myocarditis, with a lower likelihood of cardiac dysfunction at presentation and more rapid recovery ([Patel et al 2022](#)).

Long COVID, a sequela of COVID-19, affecting up to 20% of persons infected with SARS-CoV-2, has also been described in children, including in those with a mild infection. This syndrome is manifested by symptoms that can include fatigue, muscle and joint pain, insomnia, concentration difficulties, respiratory problems, persistence anosmia and ageusia, and cardiac palpitations that may occur within 6 months after infection ([Buonsenso et al 2022](#); [Buonsenso et al 2021](#); [Dembinski et al 2021](#)).

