7.5. Safety Definitions and Related Procedures

7.5.1. Adverse Event

An AE is defined as any untoward medical occurrence associated with the use of a drug in humans, whether or not considered drug related.

Events Meeting the Adverse Event Definition

- Exacerbation of a chronic or intermittent pre-existing condition including either an increase in frequency and/or intensity of the condition
- New conditions detected or diagnosed after the first dose of IP even though they may have been present before the start of the study

Events NOT Meeting the Adverse Event Definition

- Medical or surgical procedure (eg, endoscopy, appendectomy): the condition that leads to the procedure should be the AE.
- Situations in which an untoward medical occurrence did not occur (social and/or convenience admission to a hospital).

An AR is any AE for which there is a reasonable possibility that the vaccine caused the AE ([Section 7.5.9](#)). For the purposes of investigational new drug safety reporting, “reasonable possibility” means that there is evidence to suggest a causal relationship between the vaccine and the AE.

An unsolicited AE is any AE reported by the participant that is not specified as a solicited AR in the protocol or is specified as a solicited AR but starts outside the protocol-defined period for reporting solicited ARs (ie, for the 7 days after each dose of vaccine).

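### Section 7.5.9 states a reasonable-possibility standard for causality, but its two categories apply a more-likely-than-another-cause test that conflicts with Sections 7.5.1 and 7.5.11 and leaves ties unclassified

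*Protocol*

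**What the plan says.** Three places set the same standard.

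- Section 7.5.1 gives the definition: "An AR is any AE for which there is a reasonable possibility that the vaccine caused the AE". It refers the reader to 7.5.9 for the assessment. For the purpose of IND safety reporting it adds that a reasonable possibility "means that there is evidence to suggest a causal relationship between the vaccine and the AE".
- Section 7.5.11 asks the same question of the investigator for every SAE.
- The lead sentence of Section 7.5.9 asks "whether there is a reasonable possibility that the IP caused the event".

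Section 7.5.9 then gives the two categories that the investigator uses. Both open with the reasonable-possibility wording, and both then add a comparison of likelihoods. The last condition for Related is "The AE is more likely explained by the IP than by another cause". Not related lists alternatives, the last being "OR the AE is more likely explained by another cause than the IP".

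Section 7.5.9 also says that the causality assessment does not decide what is reported in the study. Section 7.5.3 treats every solicited reaction as causally related.

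**The concern.** A reasonable possibility and a balance of probabilities are different thresholds. A vaccine can be a reasonable possible cause of an event without being the likeliest one. The protocol defines an adverse reaction by the lower threshold and then gives sites categories that work at the higher one.

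Relatedness is used in several places:

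- **Table 8 (Section 8.5.2):** the rows for treatment-related AEs, treatment-related SAEs and treatment-related severe AEs.
- **Table 5 (Section 6.4):** a related SAE or related Grade 4 AE in one participant meets pause rule 2 in Part 1A. In later parts the pause rules do not apply, but the sponsor still informs the DSMB of such events.
- **Section 6.2:** one of the criteria for withholding further injection depends on the investigator judging a severe AE to be related.

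If different sites follow different sentences of Section 7.5.9, these outputs mix two standards. If all follow the categories literally, the outputs describe a narrower class of event than Section 7.5.1 defines.

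**Working it through.** The point concerns a definition, so the check is to run three kinds of unsolicited event, each with plausible timing and documented exposure, through both rules.

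| Event | Reasonable-possibility rule (7.5.1, 7.5.11, lead sentence of 7.5.9) | Categories of 7.5.9 as written |
|---|---|---|
| Vaccine is the likeliest cause | Related | Related |
| Vaccine is a reasonable possibility, another cause is likelier | Related | Not related |
| Vaccine and another cause equally likely | Related | Neither likelihood clause is met |

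**Could the likelihood clause be mere description?** Not in the category Not related. There it follows an OR, so it is sufficient alone: "the AE is more likely explained by another cause than the IP" settles the answer whatever the reasonable possibility.

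**Direction.** Related under 7.5.9 requires a reasonable possibility and, in addition, that the vaccine be the likelier cause. The second condition can only remove events from the set defined by the first. Any discrepancy therefore runs towards fewer related events.

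**Size.** Section 1.2.2.5 gives the long-term safety figures for mRNA-1273 recipients in this study, and the percentages reproduce:

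- participants with SAEs: 22/2577 = 0.85% (stated 0.9%), none judged related;
- participants with MAAEs: 1002/2577 = 38.88% (stated 38.9%);
- participants with related MAAEs: 26/2577 = 1.01% (stated 1.0%).

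These figures give logical bounds only. Under the broader rule, the number of participants with a related SAE lies between 0 and 22, and the number with a related MAAE between 26 and 1002. The protocol gives no causality probabilities, so nothing narrows these ranges. The upper MAAE bound is not realistic: Section 7.5.4 records every confirmed symptomatic COVID-19 case as a MAAE, and Section 1.2.2.5 attributes the MAAE incidence to the Omicron surge. Many of the 1002 − 26 = 976 other participants may simply have had COVID-19.

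**The case against.** The strongest reply is that little depends on the wording. Causality does not decide what is reported, and Section 7.5.10 requires all AEs regardless of relationship. Solicited reactions count as related by rule. Table 8 also tabulates AEs, SAEs, AESIs, MAAEs and severe AEs without regard to cause. Pause rules bind only in Part 1A. Section 6.2 also lists any AESI, and AEs or SAEs that in the investigator's judgment require withdrawal whatever their cause. Both categories of 7.5.9 open with the reasonable-possibility wording, so an investigator might apply that and ignore the rest. The gloss in 7.5.1 on the meaning of the term is limited to IND safety reporting.

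These limits stand and define the scope: only the related/not-related split of unsolicited events is exposed. They do not remove the contradiction. It does not depend on the IND gloss, because the definition of an adverse reaction, the SAE question in 7.5.11 and the lead sentence of 7.5.9 all use the lower threshold without it.

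Two stronger readings are tempting, and the protocol does not support either.

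- **Part 3 is hit hardest because its primary population is SARS-CoV-2 positive and so always has a rival cause.** Baseline-positive status (note to Table 7) can rest on nucleocapsid serology alone, so past infection qualifies. Section 4.1.2 excludes Part 3 participants with known infection or known close contact within 90 days before the dose. The baseline-positive subset is the Day 29 immunogenicity population; safety uses the Safety Set, which is not restricted by serostatus.
- **Vaccine-associated myocarditis would be missed.** Section 1.1 says that "the frequency of myocarditis due to COVID-19 is higher than that of vaccine-associated myocarditis", but that is population background and not a rule for a single case. Suspected cases are AESIs (Section 7.5.5.1) and all go to the independent adjudication committee (Section 7.6.2). Section 10.4 requires AESIs to be reported even in the setting of a COVID infection. None of this depends on the investigator's causality entry.

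**Conclusion.** The contradiction holds. Section 7.5.9 conflicts with its own lead sentence and with Sections 7.5.1 and 7.5.11, and it has no answer for an event with equally likely causes. Where sites apply the categories as written, unsolicited events classed as related will tend to be too few. The outputs affected are the three treatment-related rows of Table 8, the related SAE or Grade 4 AE event in Section 6.4, and the related-AE criterion in Section 6.2. Solicited reactions, all-causality counts, AESI reporting and cardiac adjudication are not affected.

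The direction follows from the definitions alone. That an effect occurs at all rests on the assumption that investigators follow the category text over the lead sentence, which the protocol does not settle. A reader might infer from the 26 related MAAEs, or from the absence of related SAEs, that a particular number was lost. The documents do not support any such figure: every reclassification rate would be a guess, and these data concern mRNA-1273, not the Part 3 vaccine.

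**What to change.** In Section 7.5.9, delete the likelihood clause from each category. Related then means that there is a reasonable possibility that the IP caused the event, with exposure and plausible timing. Not related means that there is no reasonable possibility. This brings 7.5.9 into line with its lead sentence, 7.5.1 and 7.5.11, and ties resolve as Related whenever the vaccine is a reasonable possibility.

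The cost is a change of wording and a note to sites. Related counts may rise slightly. Much of the study's data, including the Part 3 interim analysis (cutoff 05 Jun 2023), was collected before any such change, so events classified before it rest on the present wording. The CSR should say so.
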